- Women with other causes of chronic pelvic pain including infectious, gastrointestinal, psychological disorders, fibromyalgia and chronic fatigue syndrome based on review of medical history within 1 year of first study visit
- untreated severe cervical dysplasia or other gynecologic condition*
- clinically significant abnormalities on physical or laboratory examinations that require evaluation or treatment or that would make participation unsafe.*
- Hysterectomy and bilateral salpingo-oophorectomy
- Pregnancy
- Lactation
- Allergy to albumen or botulinum toxin
- Presence of antibodies to botulinum toxin or loss of response to previous injections for any indication
- A known neuromuscular junction disorder such as myasthenia gravis or Eaton-Lambert syndrome
- History of urinary or fecal incontinence
- Known pelvic prolapse

**Eligibility will be based on a physical exam at NIH at the first study visit, as well as history and available medical records within 1 year before the study visit. Negative test results will be documented to confirm study eligibility. If the Pap and the GC and chlamydia tests were not done outside of the NIH within the previous year, or if documentation of the negative test results is not available, we will await the results of the screening tests done at the NIH before administering the study medication.*

C. Criteria for withdrawal of subjects from the study

- Inability to perform home monitoring or comply with study visit schedule
- Occurrence of an adverse event that precludes further participation in the study at the discretion of the investigator
- Subject wishes to terminate participation

- Incontinence of urine or feces, or pelvic organ prolapse occurring after injection

D. Study discontinuation

- If more than 2 subjects develop incontinence or pelvic prolapse, the study will be discontinued.

V. Study procedures

A. Screening process: Women with at least a three-month history of pelvic pain suggestive of endometriosis and who have a surgical diagnosis of endometriosis will be considered for this study. Eligible women will complete written consent via telephone interview and will complete a baseline screening questionnaire (appendix 1), one month calendar (appendix 2), and submit records confirming surgical diagnosis.

B. Pre-injection medical evaluation:

This will occur in an outpatient area at the Clinical Center and will include the following for all patients:

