Women who undergo a second injection at the 1 month visit or at any time later within the 1 year follow-up period with the same pretreatment medication, precautions, injection technique, and follow-up as with the first injection. If this injection occurs outside of a scheduled visit, a new baseline will be established to include completion of Standardized Pelvic Pain questionnaire, standardized endometriosis QOL questionnaire, Rome criteria III for Irritable Bowel Syndrome, Painful Bladder Syndrome and PROMIS HRQL measures of sleep, fatigue, anxiety and depression, BPI body territories list, SF 36 Health Survey, Oswestry Disability Score and pain catastrophization scale. All subjects will receive botulinum toxin if a second injection is needed regardless of the randomization group. On the day of botulinum toxin injections, women who have not had a hysterectomy and who are sexually active will have a urine pregnancy test to exclude pregnancy. Women will be asked if they have had urinary or fecal incontinence or pelvic organ prolapse. Those experiencing these symptoms will be systematically assessed and, if significant, will not have an injection. Hormonal treatments and pain medications will be reviewed. One month later, several questionnaires will be completed including: Standardized Pelvic Pain questionnaire, standardized endometriosis QOL questionnaire, Rome criteria III for Irritable Bowel Syndrome, Painful Bladder Syndrome and PROMIS HRQL measures of sleep, fatigue, anxiety and depression BPI body territories list, SF 36 Health Survey, Oswestry Disability Score and pain catastrophization scale. Patients may come for an optional study visit at the one month time point.

Although only the results of the randomized injection will be used for statistical analyses, descriptive data on pain relief will be collected on the outcome of the second injection using the one month calendar of pain and medication use, and botulinum toxin patient response inventory.

F. Mid- and End-Study follow-up

Although only the results of the randomized injection will be used for statistical analyses, descriptive data on pain relief will be collected on the outcome of the additional injection using the one month calendar of pain and medication use, and the botulinum toxin patient response inventory. Additionally, at the mid-way (5-8 months) and study end (11-14 months) study visit,

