At the study visits, women will complete questionnaires describing their amount and frequency of pain, side effects, and the effect of the pain on their quality of life. Some subjects may find these types of questions make them feel uncomfortable. Completing these questionnaires will take about 20 minutes of the patient's time. Evaluation of injection outcome using rating scales may be slightly inconvenient, but presents no medical risk.

2) Transvaginal injection

Transvaginal injection can be painful and can cause bruising. Injection discomfort will be minimized by the use of a topical analgesic applied to the vaginal mucosa and an oral anxiolytic. Sterile technique will be used to diminish the remote risk of infection from injection.

3) Botulinum toxin

Botulinum toxin has been used since 1977 and is considered safe by the American Academy of Neurology, and an NIH-sponsored consensus conference [31, 32]. The main adverse effect associated with botulinum toxin injection is more weakness than intended in the injected or adjacent muscles. Such weakness usually improves within 1-2 months of injection. With pelvic muscle injection, the anal or urethral sphincter could possibly be weakened with resultant incontinence. Sphincter weakness is very unlikely with the dose of toxin to be used here and was not seen in the studies cited above, except in a single woman with known prior urinary incontinence. Women with a history of either bowel or bladder incontinence will be excluded

from this study. If incontinence were to occur, it would be transient, resolving over 3 weeks.

A single case report described an ischiorectal fossa abscess following botulinum toxin injection into the obturator internus and pubococcygeus muscles for refractory pelvic pain. The abscess resolved with intravenous antibiotics, incision and drainage. In that case, the injection was done without ultrasound or EMG guidance to assure needle placement in muscle. To avoid infection and abscess in our patients, the vaginal site of injection will be cleaned prior to injection and EMG guidance will be used each time to assure proper needle placement for intramuscular injection.[33]

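### Section V.E bars the second injection for incontinence or prolapse only if it is significant, while IV.C and IV.D act on any such event

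*Combined protocol and SAP*

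**What the plan says.** Three rules in the combined protocol and SAP deal with the same event.

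- **IV.C, withdrawal of subjects**, lists as a criterion: "Incontinence of urine or feces, or pelvic organ prolapse occurring after injection". It sets no severity or duration and leaves nothing to judgement.
- **IV.D, study discontinuation**: "If more than 2 subjects develop incontinence or pelvic prolapse, the study will be discontinued". This too is unqualified.
- **V.E, second injection**: "Women will be asked if they have had urinary or fecal incontinence or pelvic organ prolapse". The next step is: "Those experiencing these symptoms will be systematically assessed and, if significant, will not have an injection".

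V.E also fixes what the second injection contains: "All subjects will receive botulinum toxin if a second injection is needed regardless of the randomization group". The word *significant* is not defined or graded in V.E or elsewhere in the supplied text, and V.E does not refer to IV.C or IV.D.

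**The concern.** A woman who reports mild leakage, or leakage that has stopped, falls under two rules that point in different directions. Under IV.C she meets a withdrawal criterion. Under V.E she can be given another 100 U if someone judges the symptom not significant. Staff at the re-injection visit have V.E in front of them, and nothing there sends them back to IV.C.

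What is at stake is the safety of individual women and the consistent handling of an event that the protocol treats as serious enough to stop the trial. The treating gynecologist and the neurologist are blinded (V.C), so they cannot work out which women would be receiving toxin for the second time. The rule therefore has to be right for every woman, whatever her arm.

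**Working it through.** The protocol gives no figure to reproduce on this point. The check is a comparison of the rules, followed by simple arithmetic on timing, dose and numbers.

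**1. The rules applied to one case.** Take a woman with confirmed but mild or resolved incontinence after the first injection.

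| Rule | Qualifier | Result |
|---|---|---|
| IV.C | none | meets a withdrawal criterion |
| IV.D | none | counts towards the limit; a third such woman stops the study |
| V.E | significant, undefined | may be injected if judged not significant |

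The first and third rows cannot both be followed. IV.C does allow for judgement in one place, but that wording belongs to the general adverse-event criterion, not to this one.

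**2. Which reading fits the rest of the protocol.** The exclusion criteria in IV.B rule out any history of urinary or fecal incontinence, with no severity limit. The risk section, IX.B.3, cites the exclusion of women with incontinence as part of its support for a cumulative 200 U. Both favour the unqualified rule.

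**3. Is a resolved episode foreseeable?** IX.B.3 says: "If incontinence were to occur, it would be transient, resolving over 3 weeks". Section III puts the one-month visit at 4-7 weeks. If leakage begins soon after injection (assumption), the gap between resolution and that visit is:

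- 4 - 3 = 1 week at the earliest
- 7 - 3 = 4 weeks at the latest

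Leakage that has already stopped is thus the presentation the protocol itself predicts at the first opportunity for re-injection.

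**4. Has a first toxin dose worn off by then?** On unintended weakness, IX.B.3 says: "Such weakness usually improves within 1-2 months of injection". The Introduction puts recovery from an injection at about 3 months, or roughly 13 weeks. The time still to run at the 4-7 week visit is:

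- 13 - 7 = 6 weeks
- 13 - 4 = 9 weeks

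The end of leakage therefore does not show that the first dose has worn off. A second injection later in the year leaves less of this overlap, or none.

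**5. Dose.**

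- Toxin arm: 100 U + 100 U = 200 U
- Placebo arm: 0 U + 100 U = 100 U, so there is no earlier toxin to add to

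**6. Number of women.** VII.B allows 30 to be randomised, so about 30 / 2 = 15 receive toxin first. The documents give no event rate. With an assumed risk of 1% to 10% after the first injection:

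- 15 x 0.01 = 0.15 women
- 15 x 0.10 = 1.5 women

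This is an upper view of the repeat-toxin problem. It shrinks further to those whose episode is mild or resolved and who choose re-injection while the first dose is still active.

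**The case against.** The strongest reply is that the rules run in sequence. IV.C decides who remains in the study; V.E is a check on the day of injection for women who remain. V.E starts from a patient's answer to a question, so assessing her and acting only if the finding is significant can be read as verifying an unconfirmed self-report. Nothing in V.E says that milder cases stay in despite IV.C. IX.B.3 adds that many patients receive 200 U or more in one session. It also says that sphincter weakness did not occur in the cited studies apart from one woman with earlier urinary incontinence, a group excluded here. Section XVIII refers to a DSMB Charter for the monitoring plan, which was not available for this review.

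Much of this stands. The verification reading is plausible and would remove the conflict, and the dose argument answers a general worry about 200 U. It does not speak to women who leaked after the first dose. The verification reading is also not what V.E says: the test is significance, not confirmation. V.E points to no other document for a definition.

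Three stronger inferences are tempting and are not supported:

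- **That V.E exempts resolved episodes**, because it asks about the past and then acts in the present tense. In ordinary reading the second sentence refers back to the women who answered yes. The point does not rest on this.
- **That the stopping rule is weakened.** With 30 women and an assumed 10% risk, the chance of three or more cases is 0.589 if all are counted and 0.188 if only half are. That loss arises only if the V.E qualifier is carried into IV.D, and IV.D contains no such qualifier.
- **That 200 U is unsafe in this trial.** The protocol calls that cumulative dose well established, and nothing in the documents contradicts it.

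**Conclusion.** The inconsistency is real on the text: V.E, read literally, permits an active injection in a woman whom IV.C withdraws. A reader might infer that the protocol intends to re-inject women with incontinence. The documents do not show that intention; they show only that V.E fails to rule it out.

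This is a minor safety-consistency correction. The protocol's own view is "Sphincter weakness is very unlikely with the dose of toxin to be used here", and at the assumed 1% to 10% risk the repeat-toxin concern reaches at most one or two women. That range is an assumption, as is onset of leakage close to the injection. The primary result is untouched: it is assessed at one month after the randomised injection, data after the second injection are descriptive, and VII.B keeps withdrawn women in the analyses. The conclusion is limited to the protocol text.

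**What to change.** In V.E, replace the condition *if significant* with *if the event is confirmed, including an episode that has since resolved*. Then add that the woman will not be injected, will be handled under IV.C and will be counted under IV.D. At the one-month visit, these steps follow completion of the primary outcome assessment, so that the endpoint is recorded before any withdrawal.

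The cost is one wording change. A few women with mild or resolved symptoms lose the optional second injection, and some later descriptive follow-up is lost with their withdrawal. IV.C already implies both.

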Assessing the symptoms of pain, endometriosis-related QOL and other measures of quality of life is an important facet of assessing improvement from an intervention such as botulinum toxin. Patient-Reported Outcomes Measurement Information System (PROMIS ®) is an NIH roadmap project establishing self-report measures of health for clinical research and practice [24, 25]. The self-reported measures are drawn from calibrated item banks measuring constructs that are prevalent in chronic illness conditions including Sleep, Fatigue, and Emotional Distress, specifically depression and anxiety. The PROMIS items were administered to a large sample representing the US general population [24] and to multiple groups with chronic diseases [18]. Items are calibrated using a T-score metric with the mean of the US general population equal to 50 and standard deviation [SD] fixed at 10 with higher scores representing more problems with the domain being assessed. Pain catastrophization, a trait associated with depression and anxiety will be assessed as high scores for catastrophization has been associated with less likelihood of improvement from an intervention[26].

Allostasis is the ability to achieve stability, or homeostasis, through change. When presented with stress (or change) over time, a cumulative physiologic effect can be seen, termed allostatic load. McEwen coined this term as a means to quantify “stress-induced damage”, also referred to as “the price the body pays for being forced to adapt to adverse psychosocial or physical situations ...”[27]. In this context, allostatic load is directly applicable to the study of pain [28], and can be calculated from measures like blood pressure, body mass index, fasting lipid panel, HbA1C, CRP, morning cortisol and DHEAS.

II. Study objective

To determine the effectiveness of botulinum toxin injection in treating pelvic pain in a cohort with pelvic floor spasm, chronic pelvic pain and a history of surgery for endometriosis.

III. Study Design and Methods

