This will be a double-blinded, randomized, placebo-controlled study to determine if botulinum toxin injection can relieve pain associated with pelvic floor spasm in women with chronic pelvic pain. We plan to study women of reproductive age with pelvic muscle spasm and pain persisting after the surgery for endometriosis. Participating women will be randomly assigned to receive either botulinum toxin or placebo (an inactive salt solution) injection. The group of women receiving placebo will serve as controls. Pregnancy tests will be assessed in women who have not had a hysterectomy at the time of botulinum toxin injection and all women will be advised not to become pregnant in the month following injection. Women will be seen again one month after the first injection to assess the effectiveness of injection. Improvement in pain after the first injection will be assessed for the primary outcome. The women will be followed for a year. All participants will be offered a single reinjection with active drug at the one month visit or later during the 1 year follow-up period if the pain returns.

The intent of this protocol is to evaluate whether botulinum toxin injection improves endometriosis-associated pain as reported by the patient and assessed by gynecology and physiatry. Patients will be seen at baseline study injection, one month after the study injection (4-7 weeks), mid-way through the study (5-8 months) and at the end of the study (11-14 months). With regards to Botulinum toxin injections, patients may receive up to 2 botulinum toxin injections (study injection of botulinum toxin or placebo and then 1 additional active botulinum toxin injection— at the one month visit or later during the year after study injection).

IV. Selection of subjects

A. Inclusion Criteria:

- Female gender
- Age between 18 and 55
- History of endometriosis at surgery
- Persistent pelvic pain for at least 3 months
- Pelvic floor spasm
- Negative pregnancy test (in women who have not had a hysterectomy)
- Willing to use reliable method of contraception for the month after botulinum toxin injection including oral contraceptives, IUD, and barrier with spermicide.
- Willing and able to give informed consent
- Willing and able to comply with study requirements

B. Exclusion criteria:

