1. A complete history including medical conditions, headaches, depression, reproductive health history regarding sexually transmitted diseases, gynecologic conditions, menstrual history, contraceptive use, current hormonal treatment for endometriosis, and pregnancy history.
2. A physical examination including a pelvic exam. The presence of pelvic muscle spasm will be assessed as part of the screening evaluation by study gynecologist.
3. Administration of standardized questionnaires to assess:
 - The presence and severity of dysmenorrhea, deep dyspareunia, and non-menstrual pelvic pain (Standardized Pelvic Pain Questionnaire). A visual analogue assessment will also be performed (Brosens,[16]) (Appendix 3)
 - The quality of life (Endometriosis Health Profile-30) will also be assessed (Jones, [17]) (Appendix 4)
 - Pelvic floor distress inventory (Barber,[29]) (Appendix 5)
 - Patient-Reported Outcomes Measurement Information System (PROMIS ®) measures of health for Anxiety, 7 item measure, Depression, 8 item measure, Fatigue, 4 item measure, Sleep Disturbance, 4 item measure [25](Appendix 6). Patient responses to the questionnaires will not be routinely reviewed during clinic visits. Therefore, we have asked the patient, to communicate directly with the study team if, at any time during her participation, she feels concerned about her mood (anxiety or depression). If a concern is identified in speaking with the patient or reviewing patient responses, the potential for additional services will be discussed.
 - Rome criteria III for Irritable Bowel Syndrome[19](Appendix 14)
 - Painful Bladder Syndrome (Parsons, [20])(Appendix 15)

- SF 36 Health Survey (Appendix 16)
 - Oswestry Disability Index (Appendix 17)
 - BPI body territories list (Appendix 18)
 - Pain Catastrophization Scale (Appendix 19)
4. Laboratory tests: CBC with differential, liver function tests, BUN, creatinine, electrolytes, sed rate, thyroid panel, ANA, Rheumatoid factor, and CPK (15 ml), Pap smear, urinalysis, urine culture, and PCR screening for gonorrhea and Chlamydia at the Clinical Center. The following laboratory tests will occur in the morning with the patient fasting: Fasting lipid panel, fasting glucose, HbA1C, CRP, am cortisol, and DHEAS. The fasting and other blood tests may be drawn on the day of other study procedures or on a separate day, at the participant's convenience.

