 5. Completing of one month's calendar of medication use and baseline pain score and baseline screening questionnaire (Appendix 1 and 2)
 6. Physiatry Assessment for central nervous system sensitization and myofascial dysfunction (Appendix 7)
 7. Patient medication guide: patients will receive the botulinum toxin a medication guide for their review (Appendix 8).

C. Injection Procedure

Eligible women agreeing to participate will be randomized to active or placebo injection. The treating gynecologist, the neurologist performing EMG monitoring, and patient will be blinded to the randomization. Injection will be performed during a clinic visit after study eligibility is confirmed. Patients will be instructed not to change any hormonal treatment of endometriosis for the one month following injection.

One hour before injection, up to 10mg of diazepam will be given orally as an anxiolytic and anesthetic cream (lidocaine 4% cream) placed on the vaginal walls. The gynecologist will perform the injection with sterile technique into areas with palpable spasm, under EMG guidance provided by a neurologist. Patients will receive either 100 U type A Botox® (onabotulinum toxin A) reconstituted with preservative-free saline or a similar volume of saline. The location and amount of toxin/saline injected will be documented using a standardized recording sheet (appendix 9). Patients will be able to leave an hour after injection but will be instructed not to drive until the effects of the sedation have worn off.

Randomization will follow a permuted block design with block sizes of 4 and 6. The Pharmacy Development Service, who will not be blinded, will assign the subject. The toxin or saline will be picked up from the pharmacy and prepared by an unblinded nurse in a private, appropriate clinic area. Syringes with the toxin in solution or saline (which are identical in appearance) will be brought to the treatment room.

On the day of botulinum toxin injections, women who have not had a hysterectomy and who are sexually active will have a urine pregnancy test to exclude pregnancy.

D. Post-injection follow-up

Subjects will be asked to complete a one month's calendar of medication use and pain score after injection.

Subjects will be contacted between 3 days and 2 weeks after injection to monitor for adverse effects including genitourinary infections and change in bowel or bladder function.

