They will be offered a botulinum toxin injection at 1 month after the first injection, and will return for follow-up clinic visit scheduled at that time. At that visit, the prior month's pain symptoms and use of hormonal treatments and pain medications will be reviewed, and a gynecological examination performed. At the one month visit, several questionnaires will be completed, including: Botulinum toxin patient response inventory (Appendix 10), Standardized Pelvic Pain questionnaire, standardized endometriosis QOL questionnaire, Rome criteria III for Irritable Bowel Syndrome, Painful Bladder Syndrome and PROMIS HRQL measures of sleep, fatigue, anxiety and depression, BPI body territories list, SF 36 Health Survey, Oswestry Disability Score, and pain catastrophization scale. For those opting for a second injection, this will be done as described below.

After the 1-month visit, the patient will be contacted every three months for up to 1 year, to determine how long any effects may have lasted.

E. Second injection

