blood pressure will be checked and a pelvic exam will be done. At the mid-way (5-8 months) and study end (11-14 months) follow-up, the following laboratory tests will occur in the morning with the patient fasting: Fasting lipid panel, fasting glucose, HbA1C, CRP, am cortisol, and DHEAS. The standardized Pelvic Pain Questionnaire and standardized endometriosis-related QOL questionnaire, Rome criteria III for Irritable Bowel Syndrome, Painful Bladder Syndrome and PROMIS HRQL measures of sleep, fatigue, anxiety and depression, BPI body territories list, SF 36 Health Survey, Oswestry Disability Score, and pain catastrophization scale will be assessed. Patient responses to the questionnaires will not be routinely reviewed during clinic visits. Therefore, we have asked the patient, to communicate directly with the study team if, at any time during her participation, she feels concerned about her mood (anxiety or depression). If a concern is identified in speaking with the patient or reviewing patient responses, the potential for additional services will be discussed.

Women who become pregnant after the study injection and one month study visit for the primary outcome assessment and remain in the study (per section B.3 below) may have an additional study assessment beyond the month 12 visit, if needed, to permit a return to baseline status after the immediate post-partum period. The assessment will include completion of study questionnaires and rating scales. An in-person examination and research blood tests (as per the 12 month visit) may also be done, if feasible. These participants may also be offered a 2nd study injection up to one year after delivery or other pregnancy outcome, if they did not have a 2nd injection earlier in the study. Procedures for the later 2nd injection will be per Section E “Second Injection” procedures (above), including data collection, a new baseline assessment, injection procedure and one month assessment.

G. Psychiatry assessment for central nervous system sensitization and myofascial dysfunction

At the study end (11-14 months), women will be assessed by the psychiatrist for signs of central nervous system sensitization and myofascial dysfunction, and will be assessed by the gynecology team.

H. Medications

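### Sensitization and allostatic load are first re-measured only after both arms have been offered active toxin, so no planned test of them isolates the randomised injection

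*Combined protocol and SAP*

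**What the plan says.** **Sensitization (outcome 7).** The pre-injection evaluation in V.B includes the "Physiatry Assessment for central nervous system sensitization and myofascial dysfunction (Appendix 7"). The next scheduled assessment is in V.G: "At the study end (11-14 months), women will be assessed by the psychiatrist for signs of central nervous system sensitization and myofascial dysfunction". Section III says pain is judged "as reported by the patient and assessed by gynecology and physiatry" but ties physiatry to no visit. V.G names a psychiatrist where V.B, III and the title of Appendix 7 name physiatry.

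**Allostatic load (outcome 13).** The Introduction says it "can be calculated from measures like blood pressure, body mass index, fasting lipid panel, HbA1C, CRP, morning cortisol and DHEAS". V.B draws the bloods before injection ("The following laboratory tests will occur in the morning with the patient fasting"). V.F repeats them late: "At the mid-way (5-8 months) and study end (11-14 months) follow-up, the following laboratory tests will occur in the morning".

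**One-month visit.** V.D lists a review of symptoms and medication, a gynecological examination and questionnaires ("At the one month visit, several questionnaires will be completed, including: Botulinum toxin patient response inventory (Appendix 10"), and so on). It lists neither the sensitization assessment nor the fasting bloods.

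**Re-injection.** Section III: "All participants will be offered a single reinjection with active drug at the one month visit or later". V.E makes it active toxin whatever the randomised arm. Women with significant incontinence or prolapse (V.E) or who are pregnant (IX.B) do not receive it.

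**Analysis.** VII.A gives outcomes 7 and 13 no time point. VII.B sends continuous follow-up variables, and also length of benefit, to t-tests or paired t-tests, and categorical secondary outcomes to Fisher's exact test, all under intent to treat. V.E and V.F each confine statistical analyses to the results of the randomised injection. V.D provides three-monthly contacts for up to a year to establish how long effects lasted.

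**The concern.** V.E and V.F promise inference about the randomised injection only. VII.B tests follow-up variables, and for outcomes 7 and 13 the only follow-up values come after the point at which the control arm may have received the active drug. With no time point and no label, a between-arm p-value on either outcome would be read as evidence for or against an effect of the injection, and the schedule supports neither reading.

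A second, smaller issue sits in the same analysis paragraph. Length of benefit is compared by t-test, with no rule for a woman still benefiting at last contact or re-injected while benefit continues.

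**Working it through.** **1. The schedule.** Scheduled post-baseline values before re-injection is offered: none for sensitization, none for the allostatic-load bloods. First later values: 11-14 months and 5-8 months respectively. The new baseline that V.E requires for an off-schedule second injection, and its one-month follow-up, contain neither.

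**2. What each analysis would estimate at 5-14 months.**
- Intent to treat: toxin first against placebo first, each followed by optional toxin. This is a valid randomised comparison, but of two strategies.
- Excluding re-injected women: selects on an event after randomisation.
- Paired tests within an arm: no concurrent control.

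**3. The plan's own figures.** The plan gives no effect size or power for outcomes 7 or 13. Its one sample size, 14 per group for the primary outcome (70% v 20%, two-sided 0.05, 80% power, VII.B), is approximately reproduced by large-sample formulas: 14.1 by arcsine, 15 pooled, and 79.1% power at 14. It is used below only as a source for possible re-injection rates.

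**4. Illustration with a lasting effect.** Inputs: 30 randomised (VII.B) with half on placebo (IX.A), so 15 per arm. Assumptions: an effect of 1.06 SD, chosen because it gives 80% power (two-sample t-test, noncentral t), and a full, lasting effect in re-injected placebo women. With placebo-arm uptake u the remaining contrast is 1.06 × (1 − u):
- u = 20%: 0.848 SD, power 61%
- u = 50%: 0.530 SD, power 29%
- u = 80%: 0.212 SD, power 9%

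If every non-improver and nobody else were re-injected, 70%/20% response implies uptake of 30% on toxin and 80% on placebo. Power is then 9% if doses do not add, or 29% if they do: 1.06 × (1 + 0.3 − 0.8) = 0.530 SD. The women not re-injected would number 15 × 0.7 = 10.5 against 15 × 0.2 = 3. With 10 or 11 v 3, power is 31-32% before any selection bias.

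**5. Illustration with a fading effect.** The Introduction describes recovery over about three months, possibly longer for pain. Assuming exponential decay with mean 3 months and no re-injection at all:
- Month 5: 1.06 × exp(−5/3) = 0.20 SD, power 8%
- Month 11: 1.06 × exp(−11/3) = 0.03 SD, power 5%

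**6. Length of benefit.** Assume exponential durations with mean m, taken from the three-monthly contacts. Cutting at c months and treating the result as complete gives a mean of m(1 − exp(−c/m)).
- 12-month cut only, true means 9 v 3: 6.63 − 2.95 = 3.68, so a 6.0-month difference appears as 3.7.
- Equal true means of 6, with 30% (toxin) and 80% (placebo) cut at a month-1 re-injection and the rest at 12 months. The cut means are 6(1 − exp(−1/6)) = 0.92 and 6(1 − exp(−2)) = 5.19. Toxin: 0.7 × 5.19 + 0.3 × 0.92 = 3.91. Placebo: 0.2 × 5.19 + 0.8 × 0.92 = 1.77. This is a false difference of +2.1 months.

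**The case against.** **The plan already limits itself.** V.E and V.F confine statistical analyses to the randomised injection and call data on the later injection descriptive, and VII.B never spells out a between-arm test of outcome 7 or 13. This is partly right. However, the descriptive label covers pain relief recorded on the calendar and response inventory, not these two outcomes. They remain listed secondary outcomes, and VII.B's general rule covers them. Appendix 7 is not shown; if its measures are categorical they go to Fisher's exact test, and the timing problem is the same.

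**The late comparison is still randomised.** True. A reader might infer that any between-arm test at 5-14 months is invalid. It is not: the strategy comparison is sound if labelled as such.

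**Re-injection may not be the main cause of lost contrast.** This stands. If the effect fades over about three months, late timing alone removes most of it, so the 61/29/9% figures apply only to a lasting effect and fit an 11-14 month measure poorly.

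**Length of benefit may come from another source.** The response inventory (Appendix 10, not shown) is completed at one month. If duration is scored only there, the 12-month calculations do not apply. The duration point must therefore be conditional.

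**The duration bias has no fixed direction.** A reader might infer that the t-test always understates the toxin advantage. The second calculation in step 6 shows that it can also create one.

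**A log-rank test on all randomised women largely repeats the primary outcome.** This also stands. With non-improvers counted as events at one month, 70%/20% response and identical durations among improvers, it rejects in roughly 52-56% of simulated trials of 15 per arm.

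**Conclusion.** The main point holds. Outcomes 7 and 13 have no scheduled value between baseline and the offer of active toxin to both arms, so no analysis of them isolates the randomised injection as V.E and V.F require. This follows from the schedule and rests on no assumed figure. The size does rest on assumptions: re-injection uptake, the 1.06 SD effect and its persistence are not in the documents, and the power figures only show that the loss can range from moderate to nearly complete.

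The duration point holds only if the three-monthly contacts are the source, and its direction cannot be stated in advance. Length of benefit is named in the analysis text but is not a numbered secondary outcome.

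Nothing here reaches the primary outcome, or secondary outcomes measured at one month before any second injection. The matter should be corrected, but it does not threaten the trial's main conclusion.

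**What to change.** In VII.A-B and the matching sentences of V.E and V.F:

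- **(a)** State that tests of the effect of the randomised injection on visit-measured outcomes use one-month, pre-reinjection data.
- **(b)** Label outcomes 7 and 13, and other 5-14 month data, as descriptive, or as an exploratory intent-to-treat comparison of toxin first with placebo first then optional toxin. Make no claim of effect or no effect of the injection itself. If the exploratory option is chosen, amend the V.E and V.F sentences to allow it.
- **(c)** State the source of length of benefit. If it is the three-monthly contacts, replace the t-test with a censoring-aware analysis: interval-censored, or Kaplan-Meier with log-rank if women report the date of loss. Pre-state one analysis rule for re-injection (event, or censoring at re-injection) and run the other as a sensitivity analysis. Say that including all randomised women, with non-improvers as events at one month, gives a combined response-and-duration measure that overlaps the primary outcome and must not be read as longer benefit among responders. Report duration among improvers descriptively only.
- **(d)** Reconcile III, V.B, V.D, V.G and the Appendix 7 title on when, and by which specialty, sensitization is assessed.

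The cost is wording; no new data are needed. Outcomes 7 and 13 lose the status of randomised comparisons of the injection, and the duration result will depend partly on the re-injection rule chosen.
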